**9 REPORTING**

9.1 Evaluation of Results – this simple study design, consists of only one physiological measure (that of wheal/flare) measured at 3 time points: T1=15 minutes after SPT, T2=6hr after SPT and T3=24-48 hrs. after SPT. Our power analysis calculation indicates at a confidence level of 99% and confidence interval of 1.35, we will need a sample size of n=20. No statistical analysis will be performed. No significant effect or interaction effects are anticipated hence the small sample size.

9.2 Interim Reports – unexpected findings will be reported to the Sponsor. At the conclusion of the study, a draft report will be sent to the Sponsor and contain all of the information to be included on the final report. Comments made by the Sponsor may be incorporated into the draft report after which it will be issued as the final report and signed by the PI.

9.3 Correction or Additions to the Final Report – the sponsor will review the draft final report and make necessary edits prior to the final report being issued.

TEST ARTICLE PRECAUTIONS:

[REDACTED]

TEST ARTICLE POTENTIAL COMPLICATIONS:

[REDACTED]

TEST ARTICLE STORAGE:

[REDACTED]

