### 4 **INTRODUCTION, BACKGROUND AND OBJECTIVE**

Skin prick tests for immediate hypersensitivity have been the gold standard as assays for allergies since the 1860s and are currently used by allergists identify allergic reactions to specific allergens. These tests are minimally invasive and are used on patients of all ages from infants to seniors. They have the advantage of being highly sensitive and specific and produce rapid results.

Therapies for facilitating wound healing currently are limited especially with regard to chronic wounds and remain a significant unmet need. Chronic wounds including non-healing skin ulcers such as pressure ulcers, diabetic neuropathic ulcers and vascular insufficiency ulcers, are a source of substantial morbidity and mortality for hospitalized patients and residents of nursing homes. Non-healing and chronic wounds increase the risk of infection and can result in limb amputation and death.

Numerous topical treatments for non-healing wounds have produced mixed results and an ideal treatment remains to be achieved. The test product of this proposal, NeoMatriX™ Wound Matrix, is a wound dressing for the management of wounds, acute and chronic. NeoMatriX™ Wound Matrix has the features of a biocompatible biomaterial. Despite its stringent preparation protocols and having completed a range of biocompatibility testing, prior to utilization in human clinical trials, it remains to be tested in a small pilot study to determine if it can elicit any allergic responses. While it is highly unlikely that any study subject will have de novo, immediate allergic reactions to NeoMatriX™ Wound Matrix, the current protocol is designed to document this and determine whether study subjects may show any delayed allergic reactions.

The objective of this study is to investigate the potential of NeoMatriX™ Wound Matrix to cause an allergic response in healthy volunteers. The biomaterial is applied to the forearm of study subjects, a drop of saline solution is placed on the membrane and using a standard skin prick test device the underlying epidermis is superficially pricked through the overlying membrane. After the test, the area of the skin is observed after 15 minutes and 6 hours to see if a reaction develops. The test site will again be evaluated at 1-2 days after the initial prick test. The skin will be examined for a "wheal"—a raised, itchy bump and surrounding erythematous "flare".

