### 7.7 Grading of Test Sites - Reading Results

- Initial reading after 15 minutes looking for the presence or absence of a wheal and flare at all three sites and measuring the diameter of both the wheal and flare if present. The wheal at the positive control must exceed a wheal at the negative control by 4 mm.
- A second reading is conducted about 6 hours after the SPT administration and similar measurements are taken.
- The subjects return to the office 1-2 days after the initial administration for a third test reading and measurements.
- A positive reaction is present when there is a measurable wheal of >3 mm . Small wheals are confirmed by palpation. A flare alone is measured but is not of any clinical significance.

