### 7.8 Characteristics of Wheal and Flare

Wheals are determined by palpation or oblique lighting and the diameter is measured in mm. If the wheal is not asymmetrical two diameters are measured (smallest and largest) and an average value is calculated. Flares, areas of erythema, are similarly measured but are not considered clinically significant.

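### Protocol 9.1 presents n=20 as the result of a power analysis whose inputs are not given, then rules out any analysis, so the expected result of no reactors would carry no statement of uncertainty

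*Protocol*

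**What the plan says.** Protocol section 9.1 describes a study that "consists of only one physiological measure (that of wheal/flare) measured at 3 time points" and gives the sample size in one sentence: "Our power analysis calculation indicates at a confidence level of 99% and confidence interval of 1.35, we will need a sample size of n=20". The next two sentences read: "No statistical analysis will be performed. No significant effect or interaction effects are anticipated hence the small sample size".

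Elsewhere:
- Section 4 describes the product before its use in clinical trials: "it remains to be tested in a small pilot study to determine if it can elicit any allergic responses". The objective is the product's potential "to cause an allergic response in healthy volunteers". Section 4 also calls immediate reactions highly unlikely and says the protocol is meant to document this.
- Section 7.7 defines the outcome for each subject: "A positive reaction is present when there is a measurable wheal of >3 mm". It also sets a control requirement: "The wheal at the positive control must exceed a wheal at the negative control by 4 mm". It does not say what follows if a subject's controls fail it.
- Section 7.8 fixes the unit: "Wheals are determined by palpation or oblique lighting and the diameter is measured in mm".
- Sections 1 and 6.1 require at least 20 subjects to complete.

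**The concern.** Three statements in 9.1 do not fit together.

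1. The size is credited to a power analysis, but neither a power nor an effect size is given. A confidence level with an interval width describes at most a precision calculation, and such a calculation also needs an SD or an expected rate.
2. The size is said to rest on a 99% confidence interval, yet the following sentence rules out the analysis that would produce one.
3. A second reason is offered: the sample is small because no effect is expected. Expecting no reactions does not reduce the number of subjects needed to show that reactions are rare. The rarer the event to be excluded, the more subjects it takes.

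What is at stake is the claim the pilot report can make. A result of no reactors beside the figures 99% and 1.35 suggests a precision that the document does not support.

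**Working it through.** **Inputs.** Confidence level 99%, the figure 1.35 and n=20 come from 9.1. The unit mm comes from 7.8 and the yes/no rule from 7.7. The visible text gives no SD and no expected reaction rate, so every SD below is an assumption. The result 0/20 is inferred from the stated expectation; the protocol does not print it.

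**Step 1: can n=20 be reproduced for a mean wheal in mm?** The precision formula is n = (q × SD / h)², where q is the normal or t quantile and h the half-width. For 20 to be the smallest n that meets the width, the SD must lie above h√19/q (q for n=19) and at or below h√20/q (q for n=20). With h = 1.35:
- Two-sided 99%, t: lower bound 1.35 × 4.359 / 2.878 = 2.04; upper bound 1.35 × 4.472 / 2.861 = 2.11.
- Two-sided 99%, z = 2.576: 2.28 to 2.34.
- One-sided 99%, t: 1.35 × 4.359 / 2.552 = 2.31; 1.35 × 4.472 / 2.539 = 2.38.
- One-sided 99%, z = 2.326: 2.53 to 2.60.

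If 1.35 is the full width, h = 0.675 and every SD is halved (for example 1.02 to 1.06 for two-sided t).

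The answer depends on the missing SD. For two-sided t with h = 1.35:

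| Assumed SD (mm) | Smallest n |
|---|---|
| 1.5 | 12 |
| 2.0 | 19 |
| 2.1 | 20 |
| 2.5 | 27 |
| 3.0 | 37 |

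So 20 is attainable, but only by working back to an SD that the document does not state.

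**Step 2: what does n=20 say about the yes/no reaction of 7.7?** With no reactors among n, the exact upper limit is 1 − α^(1/n).
- One-sided 95%: 1 − 0.05^(1/20) = 13.9%.
- One-sided 99%: 1 − 0.01^(1/20) = 20.6%.
- Two-sided 99%: 1 − 0.005^(1/20) = 23.3%.

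With one reactor in 20, the one-sided 95% limit is 21.6%. With 0/25, if more subjects complete, it is 11.3%.

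**Step 3: does expecting no reactions justify a small n?** If the true reaction rate were 5%, the chance of seeing no reactor among 20 would be 0.95^20 = 36%; at 10% it would be 0.90^20 = 12%. A result of 0/20 is therefore compatible with rates that few would call rare, whatever was expected beforehand.

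**The case against.** **No arithmetic error is shown.** This is correct. On the mm reading, which is the more natural one because 9.1 names wheal and flare, an SD near 2 mm gives 20. The protocol also has blacked-out text, so the statement about missing inputs covers only what is visible, and a separate analysis plan could hold them. The sentence is still not supported where it stands, and an analysis plan that calculated an interval would contradict 9.1 as written.

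**A reader might infer that the study is far too small,** by taking 1.35 as percentage points for the reaction rate. With 20 subjects the limits above are nowhere near that. But 9.1 does not clearly mean a proportion, and section 4 calls the study a small pilot with no rarity threshold and no decision rule. The documents do not support calling 20 wrong.

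**The exclusion of analysis may mean only that no hypothesis is tested.** It stands next to a remark about effects and interactions, so this is a fair reading, and counts and measurements can still be reported. Taken literally, though, it also excludes an interval. A reader could work out the limit from n, but the report should not leave that to the reader.

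**Reporting only subjects with valid controls would add a rule.** This also stands. Section 7.7 gives no consequence for failing the 4 mm requirement, and dropping such subjects could take a true positive out of the main count. The proposed text therefore keeps every positive in it.

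**Conclusion.** The point holds as one of unsupported derivation and omitted uncertainty. From the visible text, n=20 cannot be derived. It becomes consistent with 99% and 1.35 only after assuming an SD of roughly 2.0 to 2.6 mm (1.35 as half-width) or half of that (full width), depending on sidedness and on t or z. The reason drawn from expecting no effect does not justify the number.

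The practical size is the uncertainty left unreported: for 0/20, an upper limit of 13.9% (one-sided 95%), or 20.6% one-sided and 23.3% two-sided at the protocol's own 99% level. These limits assume independent subjects and one yes/no result per subject under 7.7.

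No stated decision rests on 1.35. The point bears on what the report may conclude, and not on whether the study can run or whether 20 is acceptable for a pilot. It is a cheap improvement.

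**What to change.** Keep at least 20 completers. In section 9.1:

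1. Delete the 99% / 1.35 sentence, or specify it fully: parameter, unit, SD or expected rate, sidedness, half or full width, and method.
2. Delete the clause that explains the small sample by the absence of an expected effect. State the sponsor's actual reason for 20 (pilot size, if that is it) and the precision it gives: with 0 of 20 reacting, the exact one-sided 95% upper limit is 13.9%.
3. Replace the sentence that excludes analysis with:

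> No hypothesis will be tested. The number of subjects with a positive test-article reaction (7.7) at any reading, and at each reading, will be reported over all subjects tested and read, with the exact Clopper-Pearson one-sided 95% upper limit. Subjects whose controls do not meet the 4 mm requirement of 7.7 will be identified with all their readings. Every test-article positive stays in the count; a sensitivity result will leave out only negative subjects whose controls did not meet the requirement.

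If the sponsor prefers 99%, one level and one sidedness should be used throughout (0/20: 20.6% one-sided or 23.3% two-sided).

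**Cost.** A few sentences and a handful of exact limits, with no added subjects or procedures. The downsides are slightly more analysis work and a less favourable stated precision. The sensitivity limit can be wider still if controls fail: 14.6% for 0/19 and 15.3% for 0/18 (one-sided 95%).
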